### 9.3.3. Urinalysis

Urinalysis will be collected at visits indicated in the schedule of events ([Appendix 15.1](#)).

The following urinalysis assessments will be performed:

Appearance, bilirubin, color, glucose, ketones, leukocyte esterase, microscopy (performed if dipstick is positive; includes bacteria, casts, crystals, epithelial cells, red blood cells, and white blood cells), nitrites, occult blood, pH, protein, specific gravity, turbidity, and urobilinogen.

### 9.4. Vital Sign Measurements

Vital sign measurements will include systolic and diastolic blood pressures, pulse rate, respiratory rate, and temperature. Vital signs will be measured at visits indicated in the schedule of events ([Appendix 15.1](#)).

Height will be measured at Screening only. Weight will be measured at visits indicated in the schedule of events ([Appendix 15.1](#)).

Summary tables presenting observed values and changes from baseline will be provided for vital sign data by treatment group and combined active treatment group. Changes from baseline to each scheduled post-baseline visit will be presented.

The relevant vital sign values at each visit will be classified into the categories of low, normal, and high based on the reference ranges defined as: 60 to 100 beats/minute for pulse rate, 12 to 20 breaths/minute for respiratory rate, 36.5 to 37.5 °C for oral temperature, 90 to 140 mmHg for systolic blood pressure, and 60 to 90 mmHg for diastolic blood pressure.

Shift tables from baseline to post-baseline visits in terms of low, normal and high will be provided for pulse rate, respiratory rate and blood pressure by treatment group and combined active treatment group.

When there are multiple values within a visit for a particular vital sign variable, the worst value will be taken (worst being the smallest value for criteria below a certain threshold or the largest value for criteria above a certain threshold). If a patient has a value below the threshold and above the threshold, the value furthest from the threshold will be chosen. If the distances are the same, the value with the recent date/time will be chosen.

Unscheduled visits will be included in the calculation of baseline.

All vital sign data by patient and parameter will be presented in a listing.

## **9.5. Physical Examination**

A complete physical examination will be performed at the screening visit and an abbreviated physical examination at visits indicated in the schedule of events ([Appendix 15.1](#)).

An abbreviated physical examination will include checks of general appearance, head and neck, abdomen, lymph nodes, skin, cardiovascular system, respiratory system, and musculoskeletal system. A complete physical examination will include assessments of skin, head, ears, eyes, nose, throat, neck, thyroid, lungs, cardiovascular system, abdomen, lymph nodes, and musculoskeletal system/extremities.

Physical examination data by patient and parameter will be presented in a listing.

## **9.6. Electrocardiogram**

Electrocardiogram (ECG) assessments will include comments on the rhythm; presence of arrhythmia or conduction defects; morphology; or ST segment, T wave, and U wave abnormalities; as well as whether the tracings are normal or abnormal and if there is any evidence of myocardial infarction. In addition, the following parameters will be measured and reported: RR interval, PR interval, QRS width, QT interval, and QTcF.

The investigator will determine whether any of the ECG results are normal or abnormal and whether any abnormal results are clinically significant or not clinically significant. Clinical significance is defined as any variation in results that has medical relevance and may result in an alteration in medical care (eg, active observation, diagnostic measures, or therapeutic measures).

Summary tables will be presented for ECG data and change from baseline by treatment group and combined active treatment group. The ECG investigator interpretations will be summarized in shift tables comparing the ECG value interpretation categories of each post-baseline visit with the value at the baseline visit. In addition, the worst post-baseline ECG value will be compared with the value at the baseline visit (with worst of all being Abnormal Clinically Significant and best being Normal).

ECG data by patient and ECG parameter will be presented in a listing.

## **9.7. Bleeding Score**

Bleeding score will be summarized at visits indicated in the schedule of events ([Appendix 15.1](#)) by treatment group and the combined active treatment groups.

## 9.8. Quality of Life as Measured by the SF-36 Score

The SF-36 Score consists of 8 scales: physical function scale, role physical scale, bodily pain scale, general health scale, vitality scale, social functioning scale, role emotional scale, and mental health scale. Scale scores range from 0 to 100, with higher scores indicating better health.

Three overall scores will be further derived: physical component summary, mental component summary, and health utility score (SF-6D). The SF-6D provides a single index for use in economic evaluation or for determination of quality adjusted life years, derived from seven of the eight scales in SF-36.

All 8 scale scores, 3 overall scores, and the answer to the Global Health questionnaire item (SF-36 question 1) will be summarized by scheduled visit. Change from baseline in scale scores, physical health summary measure, mental health summary measures, SF-6D, and the Global Health questionnaire item will be analyzed and reported using the same ANCOVA model as specified for change from baseline in platelet counts in [Section 8.2.2](#), using observed cases.

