- Change from baseline in the average of the last 2 platelet counts during the treatment period
- Time to first platelet response ($>30,000/\mu\text{L}$ and $2 \times$ baseline)
- Number of subjects receiving rescue medication at least once during treatment period
- Subjects with at least one Grade 2 or higher non-skin bleeding event during treatment period.

Exploratory Endpoints:

- Peak platelet counts during the treatment period without use of rescue medication
- Bleeding score at select time points
- Quality of life as measured by the SF-36 score.

Pharmacokinetic Assessments:

Plasma PK parameters will be calculated for SKI-O-592 and its metabolites (M2 and M4) in all subjects in the PK/PD subset on Day 1 and Week 12 using a noncompartmental approach and will include the following: C_{\max} , T_{\max} , $AUC_{0-\tau}$, $t_{1/2}$, K_{el} , CL/F (SKI-O-592 only), V_z/F (SKI-O-592 only), R_{met} , and R_{AUC} , as applicable. Pharmacokinetic assessments will also be performed on Day 8 (± 2 days) for subjects in the safety run-in period only.

Pharmacodynamic Assessments:

Serial blood samples for assessment of the percentage of activated CD63+ basophils in peripheral blood will be collected in all subjects in the PK/PD subset on Day 1 and Week 12. PD parameters will include the following: E_{\max} , TE_{\max} , $AUEC_{0-\tau}$, as applicable.

Exploratory Endpoint

An assessment of PK/PD relationship between plasma concentrations of SKI-O-592, M2 and M4 and change from baseline in the percentage of activated CD63+ basophils in peripheral blood on Day 1 and Week 12

Safety Assessments:

Safety variables will include physical examination findings, vital sign measurements (systolic and diastolic blood pressure, pulse rate, respiratory rate, and temperature), ECG tracings, clinical laboratory test results (hematology, coagulation, serum chemistry, and urinalysis), bleeding score, quality of life as measured by the SF-36 score, weight, body mass index, and reporting of adverse events.

Safety monitoring will begin when subject signs the informed consent form and continue through the end-of-study visit (Week 16).

**Study Drug,
Dosage, and Route
of Administration:**

SKI-O-703 and placebo will be administered orally. Two dose levels of SKI-O-703 will be evaluated in separate groups: 200 mg BID and 400 mg BID. Third group will be of matching placebo.

Sample Size:

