7.7.4 Analysis of Secondary Endpoints

For each binary endpoint (ie, definition of subject achieving 2 or more consecutive platelet counts), a logistic regression model will be performed and include treatment, baseline platelet count and prior TPO-receptor agonist use, provided there are enough subjects in each

subgroup. The odds ratio for the treatment effect compared to placebo (together with 95% CI and p-value) will be provided.

Time to platelet response will be estimated using the Kaplan-Meier method. Each active treatment group curve will be compared against placebo curve using log-rank test. In addition, a proportional hazard model will be implemented as well with treatment, baseline platelet count, and prior TPO-receptor agonist use.

Change from baseline in the average of the last 2 platelet counts will be analyzed using an analysis of covariance with baseline platelets count as covariate, treatment, and prior TPO-receptor agonist use. Each active treatment group will be compared with placebo.

Summary statistics of the following subjects will be provided by each treatment group:

- Subjects receiving rescue medication during the treatment period
- Subjects with Grade 2 or higher non-skin bleeding event during the treatment or follow-up period

A subject will be considered to have an event if the event was observed at least once during the treatment period or follow-up period as mentioned above.

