### 4.2. Baseline Definition and Study Day

For platelet count related endpoints, baseline will be defined as the lowest platelet count within 1 month prior to or on the date that the first dose of study drug (SKI-O-703 or placebo) is taken. Data from Central lab will be used first. Otherwise, baseline will be defined as the last non-missing evaluation prior to or on the date that the first dose of study drug (SKI-O-703 or placebo) is taken.

The study day will be calculated as:

- Study day = assessment date - first dose of study drug (SKI-O-703 or placebo) date + 1, if assessment date is on or after the first dose date.
- Study day = assessment date – first dose of study drug (SKI-O-703 or placebo) date, if assessment date is prior to the first dose date.

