#### **4.4. Sample Size**

A minimum of 60 patients will be enrolled in the study. Patients will receive either 200 mg BID or 400 mg BID of SKI-O-703 or placebo in a 2:2:1 ratio.

Based on [Podolanczuk et al \(2009\)](#) at least 50% of patients in the active treatment group will be responders (R). A sample size of 24 patients per active treatment group and 12 patients in the placebo group will provide approximately 82.74% power to detect a difference between response rates of 50% and 1% in the active treatment and placebo groups, respectively, at the 2-sided 5% significance level. The test statistic used in the sample size calculation was the 2-sided Fisher's Exact test using the normal approximation method.

Patients that do not receive the study drug or do not provide at least 1 post baseline measurement will be excluded from the analysis above and replaced.

There will be no adjustment for multiple comparisons. The sample size calculation was performed using PASS 15 Power Analysis and Sample Size Software (2017). NCSS, LLC. Kaysville, Utah, USA, [ncss.com/software/pss](http://ncss.com/software/pss).

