### 8.2.2. Change from Baseline in Platelet Counts

#### *Primary Analysis*

The primary Analysis will be performed on all observed data until Week 12, regardless of rescue medication and discontinuation.

Change from baseline in the average of the last 2 platelet counts will be analyzed using an analysis of covariance (ANCOVA) model with covariates including baseline platelets count, treatment, rescue medication use, and prior TPO-receptor agonist use.

The within-group least-square (LS) means, the associate standard errors (SE), and the treatment differences in LS means, the associated SE, 95% CIs and p-values will be derived from the model to compare each active treatment group against placebo.

Descriptive statistics of baseline value, observed value and change from baseline will be presented by treatment group.

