## 14. Appendices

### 15.1. Schedule of Events

The total study duration will be 20 weeks per patients, which consists of up to 4 weeks of screening period. The treatment period will be 12 weeks (split into 1-week safety run-in period and 11-week treatment period for the first 5 patients). The post-treatment follow-up period will be of 4 weeks. Each assessment will be carried out at timepoints indicated in the Schedule of Events table and clarified in the footnotes presented below the table. The schedule of events is summarized in Table 15-1.

Table 15-1 Schedule of Events

		On-treatment Visits					Follow-up Clinic Visits	Early Withdrawal/ Unscheduled visit
	Screening (D-28 to D-1)	W1 (D1), W5 and 9 ( $\pm 3$ days)	W1D4 ( $\pm 1$ days)	W2D8 ( $\pm 2$ days)	W3, 7, 11 ( $\pm 3$ days)	W12 (D84) (EOT) ( $\pm 3$ days)	End of Study W16 ( $\pm 1$ week)	
Clinic visits	X	X a		X a*	X a	X a	X a	X
Informed consent	X							
Inclusion/Exclusion criteria	X	X h						
AEs	<----->							X
Concomitant medications	X	X		X*	X	X	X	X
Height	X							
Weight	X	X		X*		X	X	X
Physical examination/medical history b	X	X		X*	X	X	X	X
ECG c	X	X		X		X	X	X
Vital signs	X	X		X*	X	X	X	X
Urinalysis	X	X		X*	X	X	X	X
Hep B & C, HIV	X							
Pregnancy test/ FSH d	X							
Contraception status	X	X		X*		X	X	X
ABO and Rh blood type	X							
Serum chemistry	X	X		X*	X	X	X	X
Hematology, differential	X	X	X a,e	X a,e	X	X	X	X
PT/INR PTT	X					X		

		On-treatment Visits					Follow-up Clinic Visits	Early Withdrawal/ Unscheduled visit
	Screening (D-28 to D-1)	W1 (D1), W5 and 9 ( $\pm 3$ days)	W1D4 ( $\pm 1$ days)	W2D8 ( $\pm 2$ days)	W3, 7, 11 ( $\pm 3$ days)	W12 (D84) (EOT) ( $\pm 3$ days)	End of Study W16 ( $\pm 1$ week)	
Study drug dispensing		X			X			X f
Study drug administration		X	X	X*	X	X		X f
Blood samples for PK and PD assessments g		X h		X*		X		
Bleeding Score i		X		X*		X	X	X
Quality of life using SF-36 score		X				X	X	X
Pharmacogenomic screening j		X						

Abbreviations: AEs, adverse events; D, Day; ECG, 12-lead electrocardiogram; EOT, end-of-treatment; FSH, follicle stimulating hormone; hep, hepatitis; HIV, human immunodeficiency virus; PD, pharmacodynamics; PK, pharmacokinetics; PT/INR, prothrombin time/international normalized ratio, PTT, partial thromboplastin time; W, Week

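### Read literally, SAP 9.8 adjusts SF-36 change for baseline platelet count and not for the baseline value of the score itself, which costs precision on an exploratory endpoint

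*SAP*

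**What the plan says.** SAP 9.8 covers twelve outcomes: eight scales, the physical and mental component summaries, SF-6D and the global health item. Change from baseline in these is to be analysed "using the same ANCOVA model as specified for change from baseline in platelet counts in" Section 8.2.2, on observed cases. The restriction to observed cases is the only modification 9.8 makes to the borrowed model.

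The primary analysis in SAP 8.2.2 is an ANCOVA with "covariates including baseline platelets count, treatment, rescue medication use, and prior TPO-receptor agonist use". Its outcome is the change from baseline in the average of the last two platelet counts.

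The protocol gives no SF-36 model. Section 7.7.4 describes, for platelet counts only, an "analysis of covariance with baseline platelets count as covariate, treatment, and prior TPO-receptor agonist use". Section 7.7.5, on exploratory endpoints, covers peak platelet count and bleeding score. The Protocol Synopsis lists "Quality of life as measured by the SF-36 score" among the exploratory endpoints.

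A baseline SF-36 value will exist. The row "Quality of life using SF-36 score" in SAP Appendix 15.1 is marked in the column for Day 1 and Weeks 5 and 9, and again at Week 12, Week 16 and early withdrawal. For variables other than platelet counts, SAP 4.2 supplies the definition: "Otherwise, baseline will be defined as the last non-missing evaluation prior to or on the date" of first dose.

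**The concern.** In 8.2.2 the baseline covariate is the baseline of the outcome, as it should be in an ANCOVA of change. Carried to SF-36 without substitution, it becomes the baseline of a different variable. A change score depends on its own starting value: patients who start low tend to rise on retest and patients who start high tend to fall. Adjusting for platelet count cannot be assumed to remove that dependence.

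The arms are small, and SAP 4.5 stratifies only on prior TPO-receptor agonist use and platelet category, so nothing in the design balances baseline SF-36. An arm that happens to start lower will appear to improve more. SAP 9.8 is the only planned between-arm inference on quality of life, and the 8.2.2 model attaches confidence intervals and p-values to it.

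**Working it through.** **The plan's own figure.** No design figure is stated for SF-36. The only one is the power for platelet response in SAP 4.4: 82.74%, for 50% versus 1%, 2-sided 5%. It reproduces with a pooled normal approximation and continuity correction:

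- Pooled rate: (24 × 0.50 + 12 × 0.01)/36 = 0.337.
- Null SE: √[0.337 × 0.663 × (1/24 + 1/12)] = 0.167.
- Alternative SE: √(0.25/24 + 0.0099/12) = 0.106.
- Correction: 0.5 × (1/24 + 1/12) = 0.0625.
- Power: Φ[(0.49 − 0.0625 − 1.96 × 0.167)/0.106] = 82.73%.

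That figure is not in dispute and says nothing about SF-36.

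**Inputs for SF-36.** The group sizes come from SAP 4.4: "A sample size of 24 patients per active treatment group and 12 patients in the placebo group". Three inputs are assumptions and are not in the documents: equal variance σ² at baseline and follow-up; correlation r between them, taken as 0.3, 0.5 and 0.7; and remaining covariates, platelet count included, unrelated to SF-36.

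**Residual variance.** Let B be baseline, Y follow-up and C = Y − B.

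- Without own baseline: Var(C) = 2σ²(1 − r).
- The slope of C on B is −(1 − r), so with own baseline: 2σ²(1 − r) − (1 − r)²σ² = σ²(1 − r²).
- Ratio, with over without: (1 − r²)/[2(1 − r)] = (1 + r)/2.
- Extra interval width of the model as written: √[2/(1 + r)] − 1.

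**Chance imbalance.** For 24 versus 12, the SE of the baseline difference is σ√(1/24 + 1/12) = 0.354σ. Given a baseline difference d, the expected difference in change without own-baseline adjustment moves by −(1 − r)d. The last column takes d equal to one SE.

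| r | Variance without own baseline (σ²) | Variance with (σ²) | Ratio | Extra CI width | Size of shift at d = 1 SE |
|---|---|---|---|---|---|
| 0.3 | 1.40 | 0.91 | 0.65 | 24% | 0.25 SD |
| 0.5 | 1.00 | 0.75 | 0.75 | 15% | 0.18 SD |
| 0.7 | 0.60 | 0.51 | 0.85 | 8% | 0.11 SD |

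**Check by simulation.** With 2,000 simulated trials at each r, 24 versus 12 patients, and a platelet covariate independent of SF-36, the ratio of the variances of the treatment estimate was 0.65, 0.76 and 0.86, in line with the formula.

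**The case against.** The strongest reply is that the same model means the same form, with each outcome's own baseline. The covariate list in 8.2.2 is introduced as non-exhaustive, and SAP 4.2 already defines a baseline for non-platelet variables. This may well be what was intended, so the point is about the text read literally. But neither document states that reading, and SAP 1 gives pre-specification before database lock as the SAP's purpose. A programmer following 9.8 to 8.2.2 would enter the platelet count.

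The second reply is that little depends on it. SF-36 is exploratory, no decision rule or sample size uses it, and twelve outcomes are tested without multiplicity adjustment. That stands, and it limits the weight of the point.

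A reader might infer that the SF-36 treatment effect is biased. The documents do not support that for the choice of baseline covariate: randomisation makes the expected baseline difference zero, so the contrast is unbiased on average. Nor does a chance imbalance pass in full into the estimate; only the fraction (1 − r) does.

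A reader might also argue from ceiling effects, since SAP 9.8 gives a range of 0 to 100. That range is stated for the scales, not for all twelve outcomes, and a linear baseline term does not cure a ceiling.

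**Conclusion.** The point holds as a specification gap. Followed literally, the plan gives a less precise SF-36 analysis than its own data allow, and it leaves part of any chance baseline imbalance in the estimate. Under the stated assumptions, intervals are about 24% wider at r = 0.3 and 8% wider at r = 0.7. The loss shrinks as r rises, and the documents give no value for r. The consequence is confined to an exploratory endpoint.

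The same cross-reference creates two further problems:

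- The 8.2.2 outcome, an average of the last two platelet counts, has no counterpart for SF-36. The visit modelled is therefore unstated, although SF-36 is scheduled at several visits.
- The reference brings rescue medication use into the SF-36 model. That is a post-randomisation variable, and receipt of rescue is itself a secondary endpoint in Protocol 7.2.4. Unbiasedness on average, as stated above, concerns the missing baseline term only and does not extend to conditioning on rescue use.

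**What to change.** In SAP 9.8, replace the cross-reference with an explicit model. For each SF-36 score, fit an ANCOVA of change from baseline on treatment, the baseline (Day 1) value of that same score and prior TPO-receptor agonist use, on observed cases. Baseline platelet count may stay as an additional covariate.

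Two further edits should be stated openly in the SAP's section on changes to the planned analysis, because they go beyond the baseline term:

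- Name the visit analysed, for example Week 12, since the 8.2.2 outcome does not carry over.
- Leave rescue medication use out of the SF-36 model, with the reason that it is observed after randomisation.

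If own-baseline adjustment was intended all along, the new text simply records it. The cost is a short paragraph in the SAP and a small change to the model statement. No new data are needed. If platelet count is kept alongside the SF-36 baseline, the added term uses one degree of freedom. The change should be made before database lock.

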2.3 Exploratory Objectives

The exploratory objectives of this study are as below:

- To evaluate the PK/PD relationship between plasma concentrations of SKI-O-592, M2, and M4 and the percent change in activated CD63+ basophils in peripheral blood in patients with persistent and chronic ITP
- To evaluate the changes of the exploratory endpoints of select (200 mg BID and 400 mg BID) doses of SKI-O-703 compared to placebo.

[figure not shown]
3 Investigational Plan

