7.3.2 Bleeding Score

The ITP bleeding assessment score as described by [Page et al. 2007](#) will be used to characterize bleeding tendency.

Table 3 The ITP Bleeding Score Assessment

Site	Bleeding Grade		
	0	1	2
Skin [physical Examination (PE)]	None	1–5 bruises and/or scattered petechiae	>5 bruises with size >2 cm and/or diffuse petechiae
Oral (PE)	None	1 blood blister or >5 petechiae or gum bleeding that clears easily with rinsing	Multiple blood blisters and/or gum bleeding
Skin (Hx)	None	1–5 bruises and/or scattered petechiae	>5 bruises with size >2 cm and/or diffuse petechiae
Oral (Hx)	None	1 blood blister or >5 petechiae and/or gum bleeding <5 min	Multiple blood blisters and/or gum bleeding >5 min
Epistaxis	None	Blood when blowing nose and/or epistaxis <5 min (per episode)	Bleeding >5 min (per episode)
Gastrointestinal	None	Occult blood	Gross blood
Urinary	None	Microscopic (+ve dipstick)	Macroscopic

Site	Bleeding Grade		
	0	1	2
Gynecological	None (normal period)	Spotting not at time of normal period	Bleeding >spotting not at time of period or very heavy period
Pulmonary	None	N/A	Yes
Intracranial haemorrhage	None	N/A	Yes
Subconjunctival haemorrhage	None	Yes	N/A

Abbreviations: ITP, immune thrombocytopenia; PE, physical examination; N/A, not applicable

Note: In case of a breakthrough bleeding, the subjects will discontinue the trial.

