- \* Patients in the safety run-in period will have clinic visit on Week 2/Day 8 ( $\pm 2$  days) for the mentioned assessments including hematology (differential) tests. For other patients, this visit will be laboratory only visit to perform hematology (differential) tests only.
- a Clinic / laboratory visit windows are about  $\pm 3$  days for all dosing period and laboratory visits and about  $\pm 1$  week for clinic follow-up visits. The W12/D84 (EOT) visit should be performed while on therapy.
- b Complete physical examination at Screening and abbreviated physical examination at other visits.
- c For all patients: ECG on the first day of dosing and on Day 1 of each subsequent week as specified in the table above. For patients in the safety run-in only: ECG on the first day of dosing at 1, 2, 4, 8, and 12 hours after the study drug administration.
- d For women of childbearing potential only: Serum pregnancy tests are performed at Screening. FSH testing is needed for post-menopausal female patients only.
- e Laboratory only visits will be performed on Day 4 (Week 1) for all patients and on Week 2/Day 8 ( $\pm 2$  days) for patients other than those enrolled in the safety run-in period.
- f Study drug dispensing and administration can occur at unscheduled visit.
- g Samples to be collected as follows:
  - For the patients in the safety run-in period only (for PK only; no PD assessments):
    - Day 1: morning predose, 0.25, 0.5, 1, 2, 4, 8, and 12 hours (evening predose).
    - Day 8 ( $\pm 2$  days): morning predose, 0.25, 0.5, 1, 2, 4, 8, and 12 hours (evening predose).
    - Week 12: morning predose, 0.25, 0.5, 1, 2, 4, 8, and 12 hours.
  - For the patients in the PK/PD subset only (for PK/PD):
    - Day 1: morning predose, 0.25, 0.5, 1, 2, 4, 8, and 12 hours (evening predose).
    - Week 12: morning predose, 0.25, 0.5, 1, 2, 4, 8, and 12 hours.
  - For other patients not included in the safety run-in period or PK/PD subset (for PK only):
    - Week 12: morning predose.
- h Only on Day 1 (Week 1).
- i Bleeding score assessment as described by [Page](#) et al 2007 should be performed on Day 1 of each week specified in the above table and at follow-up visit.
- j A blood sample for genotyping will be drawn at baseline (Day 1, before dosing) from patients who have consented to participate in the genetic analysis component of the study.

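### SF-36 change is compared in observed cases only: the difference can be biased if withdrawal is informative and uneven between arms, and a repeated-measures model would use earlier scores that are already collected

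*SAP*

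**What the plan says.** SAP 9.8 states that the SF-36 scores "will be summarized by scheduled visit". Change from baseline is then analysed "using the same ANCOVA model as specified for change from baseline in platelet counts in" Section 8.2.2, "using observed cases". That model's terms are "baseline platelets count, treatment, rescue medication use, and prior TPO-receptor agonist use". Section 9.8 names no visit for the ANCOVA. It gives no imputation, repeated-measures model or missing-data sensitivity analysis.

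In both schedules of events (Protocol Table 2, SAP Table 15-1) the row "Quality of life using SF-36 score" is marked in the joint column for Day 1, Week 5 and Week 9, and again at Week 12, Week 16 and Early Withdrawal/Unscheduled. The footnote that limits some rows to Day 1 is not attached to this row, so the Week 5 and Week 9 assessments stand. SAP 4.3 assigns no visit windows and analyses data under the visit name on the CRF.

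The objective that SF-36 serves is comparative (Protocol 2.3): "To evaluate the changes of the exploratory endpoints of select (200 mg BID and 400 mg BID) doses of SKI-O-703 compared to placebo".

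**The concern.** An observed-case comparison at Week 12 estimates the difference among patients who still provide a score. The objective concerns the randomised groups. The two can diverge when patients leave for reasons tied to how they feel.

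The documents describe such reasons. The note under Protocol Table 3 says: "Note: In case of a breakthrough bleeding, the subjects will discontinue the trial". Protocol 4.2.1 also lists CNS bleeding, life-threatening gastrointestinal bleeding and intolerable adverse events among the reasons for withdrawal. The sample-size section assumes 50% platelet response on active and 1% on placebo, so bleeding-related loss could reasonably differ by arm. Loss of poorly faring placebo patients would make the remaining placebo group look too well and shrink the difference. Heavier loss to adverse events on active would push the other way.

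The SAP deals with the same problem for platelet change by multiple imputation, including a missing-not-at-random version (8.2.2). It has nothing equivalent for SF-36.

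**Working it through.** **Plan figures.** The documents give no effect size, dropout rate or power for SF-36. The one power figure concerns platelet response: 82.74% for 24 versus 12 patients at 50% versus 1%. A pooled two-proportion z test with continuity correction 0.5 × (1/24 + 1/12) = 0.0625 gives (0.49 − 0.0625 − 1.96 × 0.1671)/0.1060 = 0.943, hence 82.73%. The figure reproduces, but it supplies only the arm sizes here.

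**Assumptions that are not in the documents.** SD 10 points, correlation 0.6 between visits (adjacent visits in the large-sample runs), true Week 12 difference 5 points (0.5 SD), and the dropout rates shown below. No rescue process is among these assumptions, so the results indicate size and are not a forecast for the exact SAP 8.2.2 model.

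**Small-sample simulation** (24 active, 12 placebo; 4,000 trials per scenario; dropout after Week 5 or 9 more likely when the observed SF-36 change is poor):

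| Missing at Week 12, active/placebo | Observed-case ANCOVA | Repeated-measures likelihood | Observed-case shortfall |
|---|---|---|---|
| 24% / 35% | 4.64 | 5.07 | 0.36 points = 7% |
| 18% / 44% | 4.09 | 5.08 | 0.91 points = 18% |

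With nearly equal loss (31% / 28%) the two methods agree (5.07 and 4.94). A repeat under similar assumptions gave 4.1–4.8 for observed cases and 4.9–5.05 for repeated measures, with no loss of precision. The attenuation is therefore about 4% (4.8 of 5) to 18%, over dropout of about 16–26% active and 35–44% placebo.

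**Against the standard error.** The simulated standard errors are 3.53 and 3.55 points in the first scenario and 3.72 and 3.78 in the second, nearly the same for both methods. The bias is 0.36/3.53 = 0.10 and 0.91/3.72 = 0.24 of a standard error. Squared bias is about 1% (0.13 of 12.5) and 6% (0.83 of 13.8) of the variance. As a hand check with complete data, √(1/24 + 1/12) = 0.354 SD unadjusted, or 0.354 × √(1 − 0.6²) = 0.283 SD if baseline and Week 12 correlate at 0.6. With 24%/35% missing, about 18.2 and 7.8 patients remain, and √(1/18.2 + 1/7.8) × 0.8 = 0.34 SD, close to the simulated value.

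**Large-sample simulation** (300,000 per arm; bias in SD units on a true 0.5 SD; unequal rates are placebo/active 30/10, 40/20 and 50/30%):

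| Dropout depends on | Rates | Observed cases | Using Week 5 and 9 scores |
|---|---|---|---|
| Nothing, or baseline only | equal or unequal | within 0.004 of 0 | within 0.004 of 0 |
| Last observed score | equal | about 0 | about 0 |
| Last observed score | unequal | −0.046, −0.051, −0.055 (9–11%) | 0.000 to 0.002 |
| Unobserved current score | unequal | −0.103, −0.114, −0.124 (21–25%) | −0.084, −0.096, −0.104 |

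In the last row the earlier scores remove only 0.019/0.103 = 18%, 0.018/0.114 = 16% and 0.020/0.124 = 16% of the bias. At a roughly constant dropout hazard, 34–41% of patients missing at Week 12 have no Week 5 score.

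**The case against.** A reader might infer that the SF-36 difference is biased and that the Week 5 and Week 9 scores would correct it. The documents support neither statement.

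- **Bias is conditional.** In these runs it was about zero when dropout was random, followed baseline only, or followed the score at equal rates in both arms. The documents give no rate or mechanism.
- **Correction is conditional.** Full correction appears where dropout was generated from earlier observed scores, which is the condition under which a repeated-measures likelihood is valid. When dropout follows the unobserved score, most of the bias stays.
- **Missingness may be lower than assumed.** SF-36 is scheduled at Early Withdrawal. Protocol 4.2.2 asks for end-of-study assessments where possible after discontinuation, and Protocol 1.4 plans continued follow-up. This stands. However, because SAP 4.3 works by CRF visit name, no rule brings a withdrawal-visit score into a scheduled-visit comparison.
- **The bleeding route is not settled.** The Table 3 note conflicts with the note in Protocol 4.2.1, which says bleeding should not lead to removal, at least in the first 4 weeks. These must be reconciled, and the Table 3 note alone does not support dropout as high as assumed here.
- **The visit-wise comparison is inferred**, because SAP 9.8 names no visit.
- **Proportionality.** The main analysis of platelet change, a secondary endpoint, also uses observed data, with imputation only as sensitivity. Asking for a different main model for an exploratory endpoint goes further.

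These objections limit the wording and the severity. They do not remove the case for using scores that are already collected.

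**Conclusion.** The point holds as a minor one. SAP 9.8 leaves out a patient with no score at the analysed visit and makes no use of that patient's earlier or withdrawal-visit scores. If withdrawal is related to quality of life and uneven between arms, the comparison can be biased. With dropout of about 16–26% active and 35–44% placebo following earlier scores, the attenuation is roughly 4–18% of a 5-point difference, or at most about a quarter of a standard error. If dropout follows unobserved scores, attenuation in the large-sample runs was 21–25%, and a repeated-measures model helps only a little. All of this rests on assumed dropout, correlation and effect. The endpoint is exploratory, without power or multiplicity control, and the primary conclusion is not affected.

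**What to change.** In SAP 9.8:

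1. Name Week 12 as the SF-36 analysis visit.
2. Fit a mixed model for repeated measures to change at Weeks 5, 9 and 12, with treatment, visit, treatment-by-visit, the scale's own baseline value and prior TPO-receptor agonist use. Use an unstructured covariance, with a named simpler structure (for example compound symmetry) if it does not converge. Report each dose against placebo at Week 12.
3. State how Early Withdrawal SF-36 scores map to a visit.
4. Say explicitly whether the rescue-medication covariate of Section 8.2.2 is dropped for SF-36.
5. Keep the observed-case analysis as supportive. One missing-not-at-random sensitivity analysis would show how far the result depends on the model's assumption.

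The cost is SAP wording and a standard SAS procedure, with no new data. The downsides are a few more covariance parameters with only 12 placebo patients, and validity only under missing at random.
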